### 8.2.2 Patient Disposition

A detailed description of patient disposition will be provided. It could include the following:

- summary of patients entered and by site
- total number of patients entered
- total number of patients enrolled
- summary of reasons for patients entered, but not enrolled
- total number of patients treated
- summary of reasons for patients enrolled, but not treated.

A detailed summary of reasons for patient discontinuation from study treatment will be provided.

A summary of all identified important protocol violations will be provided.

### **8.2.3. Patient Characteristics**

Patient characteristics could include a summary of the following:

- patients demographics
- time of menopause
- baseline disease characteristics
- preexisting conditions/secondary conditions
- prior therapy

Other patient characteristics will be summarized as deemed appropriate.

The categorical variables will be summarized by contingency tables. The continuous variables will be described by the number of patients with valid values (n), mean, standard deviation, median and range in both arms.

The significance level of all statistical tests is established at 0.05.

The effect of the treatment on continuous variables will be assessed by paired-t analysis (or Mann-Whitney-Wilcoxon in case of lack of normality). Categorical variables will be analyzed by chi-cuadrado or Fisher's exact test.

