#### **1.4 Management of sexual adverse effects derived from the treatment of breast cancer patients**

Taking into consideration that many women diagnosed with breast cancer today will be long-term survivors of their disease, the long-term impact of therapy on their well-being and specifically on their sexual adverse effects has become a growing topic for research (9).

In order to overcome symptoms of estrogen deprivation, vaginal moisturizers or, sometimes, low dose topical estrogens are used in daily clinical practice, despite the inexistence of adequate clinical trials that support their use. Non-hormone vaginal moisturizers relieve urogenital symptoms, however their efficacy is significantly lower compared to vaginal estrogens (10). In contrast to oral hormone therapy, some consider that local application of estrogens seems to be safe in postmenopausal breast cancer patients (11). However, the report of a small prospective observation (12) advised caution with the use of vaginal estradiol in breast cancer patients receiving aromatase inhibitors, as an increase of serum estradiol levels was found that potentially could counteract endocrine breast cancer treatment (13).

A study using lower doses of estradiol presented in the 2013 ASCO Annual Meeting showed no changes in FSH while sporadic elevations of estradiol were seen in 5 out of 26 studied patients. The significance of this is difficult to judge as the full results have not been published yet (14).

According to the publication “*Practical guidelines for managing menopausal symptoms after breast cancer*”, the use of vaginal estradiol in patients treated with aromatase inhibitors was discouraged, but there was recommended the application of vaginal estriol, a much less potent estrogen than estradiol, in case estrogen therapy were deemed necessary (15).

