### 3. Investigational Plan

#### 3.1 Study Design

This is a phase II, prospective, randomized, double-blind, placebo-controlled, international (Spain and Sweden) and multicentre study.

Sixty patients will be randomized (stratified by site) to receive 0.005% estriol vaginal gel (arm A) and placebo moisturizing gel (arm B) in a 4:1 proportion, so 48 patients will enter in arm A and 12 in arm B. Patients will undergo gynaecological tests, plasma and serum extraction for hormone determinations, adverse events collection and will answer a questionnaire according to what is outlined in Figure 1.

A) Patients randomized to Arm A (experimental arm) will receive:

Investigational drug product: 0.005% estriol vaginal gel (Blissel®)

Route: Vaginal. Administration by an applicator inserted deep inside the vagina

Dose: 1 g of gel, containing 50 µg of estriol

Dosage schedule: Weeks 1-3: single daily application  
Weeks 4-12: twice weekly administration.

[figure not shown]
Women will be instructed to administer the gel at bedtime.

B) Patients randomized to Arm B (control arm) will receive:

Placebo moisturizing gel (vehicle of Blissel®).

Same route and dose schedule than Blissel®.

**Figure1.** Study Design

[figure not shown]

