## 8. Sample Size and Statistical Methods

### 8.1 Determination of Sample Size

This is an exploratory study and there are scarce data to allow a precise sample size calculation. The most relevant data come from Pfeiler(16) who reported that the levels of FSH in patients treated with aromatase inhibitors fell from a mean value of 75.7 to 66.0 mIU/ml after two weeks of daily vaginal treatment with 0,5 g of estriol. Although no figures are reported of the variability of those measurements, an estimation of the standard deviation can be made applying the standard rule of  $[sd = \text{range}/4]$ . The reported range of FSH values in that report is 45.6 – 134.6, thus a reasonable approximation to the sd is  $89/4 = 22.3$ . Under these assumptions, it can be calculated that a sample size of 44 would provide 80% power to detect with an  $\alpha=0.05$  a decrease of FSH levels from 75.7 to 66.0 mIU/ml assuming a standard deviation of 22.3.

The hormone levels in women treated with IA who are not receiving estrogen therapy are likely to suffer physiological temporal oscillations. These variations could make difficult the interpretation of any eventual modification of hormone levels observed in the estriol treated women. In the absence of data of naturally occurring variations in hormone levels of women treated with IA that allow us to interpret the results of hormone determinations under study, it is considered appropriate to include a placebo group to provide reference data. In this case, the placebo is a vaginal moisturizing gel.

It is estimated that a group of 11 women will allow the assessment of physiological fluctuations in hormone levels. Additionally, this sample size for the placebo group will provide 80% power and  $\alpha=0.05$  to differentiate between active and placebo (ratio 4:1) on the change in the vaginal maturation value, which is a secondary variable of the study that provides objective information about the effectiveness of treatment on vaginal atrophy (calculation based on the parameter data from the pivotal Blissel study and considering only the subgroup of women who had severe vaginal dryness: change VM active group 24.9 vs 0.6 points in placebo group, SD = 24.2).

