### **8.2.6. Hormone levels**

All these analysis will be based on the ITT population.

The primary endpoint and one of the secondary endpoints are to evaluate the variation from baseline of FSH, LH, estriol, estradiol and estrone blood levels in patients treated with 0.005% estriol vaginal gel/placebo.

The variation of the levels of FSH, estriol, estradiol, estrone and LH after treatment with 0.005% estriol vaginal gel will be studied in each woman. The variation of levels between two arms will be analyzed using a non-parametric test (Mann-Whitney-Wilcoxon test) or an ANCOVA (if it must be adjusted by initial value).

Two determinations of FSH and LH before treatment with 0.005% estriol vaginal gel will be studied in each woman in order to study the intra-individual variation. Screening and baseline determinations will be used for this purpose.

Changes in hormone levels will be studied in each woman along the treatment (see sections 6.1 and 6.2).

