### **8.2.7. Efficacy**

The efficacy analysis will be evaluated in the ITT population.

The primary endpoint, the variation of FSH between week12 and baseline and comparing by arm will be analyzed using a non-parametric test (Mann-Whitney-Wilcoxon test).

An ANCOVA analysis will be used to corroborate the results obtained for the primary endpoint. The ANCOVA analysis will compare the variation of FSH 12 weeks adjusted by FSH basal between the two arms. This analysis will be performed if the relation between FSH 12 and FSH basal is lineal.

The variations in the intensities for each one of the symptoms and signs of the vaginal atrophy, after 3 and 12 weeks, in each treatment arm, will be compared using the non-parametric test Mann-Whitney-Wilcoxon.

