### **8.2.9. Other Analyses: Patient Reported Outcomes: FSFI**

Sexual function measured by the FSFI scale. It will be used an algorithm for determining domain scores and a composite full-scale score. The individual domain scores and full scale score of the FSFI are derived by a computational formula outlined in the SAP. Individual domain scores are obtained by adding the scores of the individual items that comprise the domain and multiplying the sum by the domain factor. The full scale score is obtained by adding the six domain scores. It should be noted that within the individual domains, a domain score of zero indicates that no sexual activity was reported during the previous evaluation.

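### Section 8.2.3 pairs a paired t-test with Mann-Whitney-Wilcoxon as its non-normal fallback; the two are not counterparts, so one named test is wrong (minor; the primary test is unaffected)

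*Protocol*

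**What the plan says.** Section 8.2.3 (Patient Characteristics) first lists baseline descriptors and summary statistics for the two arms, and sets the significance level for all tests at 0.05. It then gives a general inferential rule: "The effect of the treatment on continuous variables will be assessed by paired-t analysis (or Mann-Whitney-Wilcoxon in case of lack of normality"). The next sentence gives the rule for the other data type: "Categorical variables will be analyzed by chi-cuadrado or Fisher's exact test".

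Elsewhere the protocol uses the same non-parametric test to compare arms. For hormones, section 8.2.6 says "The variation of levels between two arms will be analyzed using a non-parametric test (Mann-Whitney-Wilcoxon test"), with ANCOVA as the alternative. For the primary endpoint, section 8.2.7 says "the variation of FSH between week12 and baseline and comparing by arm will be analyzed using a non-parametric test (Mann-Whitney-Wilcoxon test"), with a supporting ANCOVA. Section 8.2.7 also applies Mann-Whitney-Wilcoxon to symptoms and signs. Section 8.2.7.2 compares maturation value and pH between estriol and placebo by an unnamed non-parametric test.

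Change in FSFI at weeks 3 and 12 is a secondary endpoint (section 2.4). Section 8.2.9 covers its scoring, "Sexual function measured by the FSFI scale. It will be used an algorithm for determining domain scores and a composite full-scale score", and names no test.

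**The concern.** The standard pairs are the paired t-test with the Wilcoxon signed-rank test, for change within one group, and the independent-samples t-test with Mann-Whitney-Wilcoxon, for two separate groups. Section 8.2.3 takes one member from each pair. Followed literally, a normality check could move the analysis from a within-woman question to a between-arm one, or could put an independent-groups test on paired data.

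What is at stake is the meaning of treatment effect. The control is "Placebo moisturizing gel (vehicle of Blissel®)", and section 1.4 says "Non-hormone vaginal moisturizers relieve urogenital symptoms", although that sentence goes on to call them less effective than vaginal estrogens. Section 8.1 justifies the placebo arm because hormone levels fluctuate without treatment: "These variations could make difficult the interpretation of any eventual modification of hormone levels observed in the estriol treated women". That remark concerns hormones, but the logic is general. A change seen only within the estriol arm cannot be separated from what the vehicle, or time alone, would produce.

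**Working it through.** **1. Which comparison is meant?** The protocol's statements point both ways.

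| Evidence | Points to |
|---|---|
| 8.2.3 speaks of the effect of the treatment and has just summarised the two arms | Between arms |
| 8.2.3 pairs its rule with chi-square or Fisher, which are tests for independent groups | Between arms |
| 8.2.6, 8.2.7 and the synopsis paragraph on blood hormone levels use Mann-Whitney-Wilcoxon between arms | Between arms |
| 8.2.3 names a paired t-test | Within women |
| 8.2.6 says changes are studied in each woman, with no test named | Within women |
| 8.1 derives n = 44 for a fall within the treated group (step 2) | Within women |

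The wording nearest the sentence favours the between-arm reading, which makes the paired t-test the likelier slip. No other section settles it.

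**2. The plan's own figure.** The inputs from section 8.1 are a fall of 75.7 − 66.0 = 9.7 mIU/ml, SD 22.3, alpha 0.05 (taken as two-sided) and n = 44. With 22.3 treated as the SD of change:

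- Standardised effect = 9.7 / 22.3 = 0.435.
- Noncentrality = 0.435 × √44 = 2.885, with 43 degrees of freedom and critical t = 2.017.
- Power = P(|T| > 2.017) under the noncentral t = 80.5%.

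This reproduces the stated 80%. The smallest n reaching 80% by this formula is 44. A two-sample calculation does not give 44: it needs 83 per arm at 1:1, or 52 controls at 4:1.

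**3. Illustration of the difference between the readings.** Assume that both arms change by the same amount d, in units of the SD of change, so that estriol adds nothing to the vehicle. The protocol gives no such figure for FSFI, so d is varied from 0.1 to 0.5. The number analysed in the estriol arm is 44 and the test is two-sided at 0.05. The chance that the paired t-test is significant is P(|T| > 2.017) with noncentrality d × √44.

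| d | Noncentrality | Paired t-test, estriol arm | Between-arm test on change |
|---|---|---|---|
| 0.1 | 0.663 | 9.9% | 5% |
| 0.2 | 1.327 | 25.4% | 5% |
| 0.3 | 1.990 | 49.4% | 5% |
| 0.4 | 2.653 | 73.7% | 5% |
| 0.5 | 3.317 | 90.0% | 5% |

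The last column stays at 5% because an equal change in both arms is the null hypothesis of the between-arm test. The paired test is not faulty as a test: it correctly detects a change from baseline. The error would lie in calling that change the effect of estriol.

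**4. What the sentence can reach.** The hormones (8.2.6), FSH at week 12 and symptoms and signs (8.2.7), and maturation value and pH (8.2.7.2) have their own rules. What remains is any continuous endpoint for which the protocol names no test. FSFI change is the evident candidate.

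**The case against.** The sentence stands under Patient Characteristics, while FSFI has its own section. Section 8.2.1 leaves detailed methodology to the SAP, which is not at hand, and a test for a secondary questionnaire is commonly set there. This stands as far as FSFI goes: nothing says that 8.2.3 governs it, so the most that can be said is that it could. It does not rescue the sentence, because baseline characteristics cannot show an effect of treatment, so the rule must be meant for post-treatment data. The fault is also a wrongly named pair of tests, not a detail left for later.

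The harm in step 3 also needs several things together: a within-arm reading, an endpoint with no rule of its own, and reporting of the result as estriol's effect. On the likelier between-arm reading, the paired t-test is only a naming slip and this harm does not arise. That is fair, and it is why the figures are an illustration and not an estimate.

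Two stronger inferences are tempting. One is that the primary analysis is compromised; section 8.2.7 fixes it separately as a between-arm test, so it is not. The other is that the within-arm derivation of n = 44 shows which reading 8.2.3 intends, or adds weight to this point. That derivation concerns FSH, whose test is fixed elsewhere, and it cannot decide what a general sentence in 8.2.3 means.

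**Conclusion.** The sentence is wrong as written, and the point is minor. That the two named tests are not counterparts is certain. That the paired t-test is the slip is likely from the context but not settled by the text. That FSFI is affected is only possible, and depends on the SAP.

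The 10% to 90% range against 5% rests on an assumed equal change in both arms of 0.1 to 0.5 SD of change, 44 women analysed in the estriol arm and approximately normal changes. It shows why the two readings must not be interchanged; it does not predict this trial's error rate. The primary FSH test, the other endpoints with their own between-arm rules, and the sample size are not affected.

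**What to change.** Replace the sentence in 8.2.3 with one that defines the effect of treatment as the between-arm comparison of change from baseline, tested by an independent-samples t-test, or by Mann-Whitney-Wilcoxon if the changes are not normal. If within-arm change is also reported, name the paired t-test, or the Wilcoxon signed-rank test if the changes are not normal, and label the result descriptive and not the treatment effect. It would help to say which endpoints the rule covers, and whether FSFI change is among them or is left to the SAP.

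The cost is one or two sentences, best settled before unblinding. Sections 8.2.6 and 8.2.7, the primary analysis, the sample size and the data collection stay as they are.

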### **8.2.4. Concomitant Therapy**

A summary of concomitant therapies will be generated in the safety population.

### **8.2.5. Treatment Compliance**

The percentage of complying patients will be calculated at weeks 3, 8 and 12, defined as those with a compliance percentage of 80-110%, in the group of patients treated with 0.005% Estriol vaginal gel and in the placebo group. The overall compliance of the study drug will be calculated from these partial calculations. It will be summarized the patients and reasons of those patients which did not complete the 80% of medication of the study.

### **8.2.6. Hormone levels**

All these analysis will be based on the ITT population.

The primary endpoint and one of the secondary endpoints are to evaluate the variation from baseline of FSH, LH, estriol, estradiol and estrone blood levels in patients treated with 0.005% estriol vaginal gel/placebo.

The variation of the levels of FSH, estriol, estradiol, estrone and LH after treatment with 0.005% estriol vaginal gel will be studied in each woman. The variation of levels between two arms will be analyzed using a non-parametric test (Mann-Whitney-Wilcoxon test) or an ANCOVA (if it must be adjusted by initial value).

Two determinations of FSH and LH before treatment with 0.005% estriol vaginal gel will be studied in each woman in order to study the intra-individual variation. Screening and baseline determinations will be used for this purpose.

Changes in hormone levels will be studied in each woman along the treatment (see sections 6.1 and 6.2).

### **8.2.7. Efficacy**

The efficacy analysis will be evaluated in the ITT population.

The primary endpoint, the variation of FSH between week12 and baseline and comparing by arm will be analyzed using a non-parametric test (Mann-Whitney-Wilcoxon test).

An ANCOVA analysis will be used to corroborate the results obtained for the primary endpoint. The ANCOVA analysis will compare the variation of FSH 12 weeks adjusted by FSH basal between the two arms. This analysis will be performed if the relation between FSH 12 and FSH basal is lineal.

The variations in the intensities for each one of the symptoms and signs of the vaginal atrophy, after 3 and 12 weeks, in each treatment arm, will be compared using the non-parametric test Mann-Whitney-Wilcoxon.

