**Study Design and Treatment:**

This is a phase II, prospective, randomized, double-blind, placebo-controlled, international (Spain and Sweden) and multicentre study.

60 patients will be randomized to receive 0.005% estriol vaginal gel (arm A) and placebo moisturizing gel (arm B) in a 4:1 proportion, so 48 patients will enter in arm A and 12 in arm B.

**Arm A:** Investigational drug product: 0.005% estriol vaginal gel (Blissel®)

Route: Vaginal. Administration by an applicator inserted deep inside the vagina

Dose: 1 g of gel, containing 50 µg of estriol

Dosage schedule: Weeks 1-3: single daily application  
Weeks 4-12: twice weekly administration.

Women will be instructed to administer the gel at bedtime.

**Arm B:** placebo moisturizing gel administered in the same way.

Patients will have hormone determinations (estriol, estradiol, estrone, FSH and LH) analyzed in a central laboratory at baseline and at weeks 1, 3, and 8 from the beginning of the therapy and at week 12 (last day of study therapy). An additional FSH and LH determination will be obtained during the screening period in order to assess the intra-individual variation of these hormones in baseline conditions. Patients will also undergo gynaecological examination (vaginal smear and pH), evaluation of vaginal symptoms and signs, and will answer a female sexual function questionnaire at baseline, at week 3 (from the beginning of therapy) and week 12 (last day of study therapy). Adverse events will be followed along the study and specifically collected at weeks 1, 3 and 8 from the beginning of therapy, at week 12 (last day of study therapy) and at safety visit (30 ±5 days after last day of study therapy).

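### The synopsis and 8.2.6 leave the primary FSH between-arm test open between Mann-Whitney and ANCOVA, while 8.2.7 fixes Mann-Whitney; one unconditional test should be stated, and the pre-dose FSH already collected could sharpen it

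*Protocol*

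**What the plan says.** Section 8.2.7 is explicit: "The primary endpoint, the variation of FSH between week12 and baseline and comparing by arm will be analyzed using a non-parametric test (Mann-Whitney-Wilcoxon test". It then says "An ANCOVA analysis will be used to corroborate the results obtained for the primary endpoint", and attaches a condition: "This analysis will be performed if the relation between FSH 12 and FSH basal is lineal". No criterion for linearity is given.

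Section 8.2.6 opens with "The primary endpoint and one of the secondary endpoints are to evaluate the variation from baseline of FSH, LH", so it covers the primary endpoint as well as the secondary hormones. For the between-arm comparison it offers Mann-Whitney "or an ANCOVA (if it must be adjusted by initial value". The synopsis paragraph on blood hormone levels carries the same alternative. Neither says when adjustment is required.

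Section 8.2.3, under Patient Characteristics, has a general sentence: "The effect of the treatment on continuous variables will be assessed by paired-t analysis (or Mann-Whitney-Wilcoxon in case of lack of normality".

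FSH is measured twice before dosing. The synopsis explains the extra sample: "An additional FSH and LH determination will be obtained during the screening period in order to assess the intra-individual variation of these hormones". Section 8.2.6 confirms that use: "Screening and baseline determinations will be used for this purpose". Only the baseline value enters the primary comparison.

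**The concern.** The protocol describes one comparison by two rules. One fixes the test. The other leaves a choice, under a condition that could be settled after the data are seen. If the looser rule were followed, the primary p-value could come from whichever of two tests looked better.

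There is also a question of sensitivity. Section 8.1 names natural oscillation of hormone levels as the main difficulty of interpretation. A change from one baseline reading carries that reading's full fluctuation, although a second pre-dose reading is available. The hypothesis in 1.6 is that gonadotropins do not decline significantly, so an insensitive test errs towards the hoped-for answer.

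**Working it through.** **Inputs.** From 8.1: fall 75.7 − 66.0 = 9.7 mIU/ml; SD 89/4 = 22.3; 44 active and 11 placebo evaluable. Alpha is 0.05 (8.2.3), taken as two-sided. The protocol gives no within-woman correlation r, so r is assumed and shown as a range.

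**1. The plan's own figure.** For a one-sample (paired) test, n ≈ (1.96 + 0.842)² / (9.7/22.3)² = 41.5. With the t distribution, 44 is the smallest n reaching 80% (power 80.5%). So n = 44 reproduces, but as a within-arm test. For the between-arm contrast, with 22.3 read as the SD of change, SE = 22.3 × √(1/44 + 1/11) = 7.52 and 9.7/7.52 = 1.29. A two-sample t-test then has 24.5% power.

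**2. Cost of an open choice.** In simulated trials, Mann-Whitney on change was set against single-baseline ordinary ANCOVA (normal data, all visits equally correlated, 22.3 read as the SD of one FSH value):

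| r | Either significant, no effect | Disagree at fall of 9.7 |
|---|---|---|
| 0.5 | 7.6% | 16.4% |
| 0.8 | 6.6% | 14.2% |
| 0.9 | 6.1% | 8.8% |

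Heavy-tailed noise, t(3), raises these to at most 7.9% and 19.4%.

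**3. What the pre-dose values could add.** Residual variance as a fraction of SD², equal correlation:
- change from baseline: 2(1 − r)
- ANCOVA on one baseline: 1 − r²
- change from the two-value mean: 1.5(1 − r)
- ANCOVA on the two-value mean: 1 − 2r²/(1 + r)

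At r = 0.8 these are 0.40, 0.36, 0.30 and 0.289. Averaging the two values accounts for most of the gain.

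Simulated power (%), 44 vs 11, normal data. A pair gives the correlation between the two pre-dose values, then that of each with week 12:

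| Correlation | Planned Mann-Whitney | Mann-Whitney, two-value mean | HC3 ANCOVA, one baseline | HC3 ANCOVA, two-value mean |
|---|---|---|---|---|
| 0.5 | 23.2 | 29.5 | 29.1 | 32.2 |
| 0.7 | 35.1 | 43.7 | 38.6 | 45.1 |
| 0.8 | 48.8 | 60.1 | 51.8 | 60.8 |
| 0.9 | 76.9 | 87.8 | 78.2 | 87.6 |
| 0.9, 0.5 | 22.4 | 23.3 | 29.4 | 29.4 |
| 0.9, 0.7 | 34.5 | 37.2 | 39.0 | 40.4 |
| 0.9, 0.8 | 50.1 | 54.5 | 53.2 | 56.6 |
| 0.95, 0.9 | 77.7 | 82.9 | 78.7 | 83.1 |

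Across separate runs the two-value HC3 ANCOVA gains about 5-13 points. The two-value rank test gains 6-13 with equal correlation, but only 1-6 when week 12 is less correlated.

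**4. Where the gain fails.**
- *Screening tracks week 12 less well than baseline.* Write r12, r13 and r23 for the screening-baseline, screening-week 12 and baseline-week 12 correlations. Two-value ANCOVA then leaves 1 − [(r13 + r23)/2]² / [(1 + r12)/2]. At (0.9, 0.81, 0.9) this is 1 − 0.855²/0.95 = 0.230, against 0.20 for change from baseline and 0.19 for single-baseline ANCOVA. Change from the two-value mean leaves 1 + 0.95 − 1.71 = 0.24, so the rank version shares the weakness. Simulated power, planned test vs two-value HC3: 79 vs 72% here, and 48 vs 48% at (0.9, 0.72, 0.8).
- *Heavy-tailed noise, t(3), equal correlation.* Planned test vs two-value HC3: 51.2 vs 55.2% at 0.7, 67.6 vs 69.4% at 0.8, 92.0 vs 89.5% at 0.9. The two-value rank test reaches 62.2, 78.1 and 96.7%. Single-baseline HC3 ANCOVA can lose up to 11 points (90.9 vs 80.0% with 10% of readings at four times the noise, r = 0.9).

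**5. Why HC3.** If placebo week-12 noise SD is 1.5 or 2 times that of the active arm, ordinary least-squares ANCOVA on the two-value mean has type I error 9-11% or 14-16%. The planned Mann-Whitney has 6-7% or 8-9%, and HC3 stays at 4.5-6.0%.

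**The case against.** The strongest reply is that the primary test is already identifiable. Section 8.2.7 names it and gives ANCOVA a supporting role. The synopsis and 8.2.6 can be read as general text for five hormones at several visits. This largely stands: the planned Mann-Whitney is a valid test, and the 6-8% error rate arises only if the looser wording is used. It does not remove the need to align the sections, because 8.2.6 names the primary endpoint.

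Three stronger readings are tempting and not supported:
- A reader might infer that the linearity condition decides the primary test. It controls only the supporting ANCOVA.
- A reader might take the paired-t sentence in 8.2.3 as a third rival rule. It sits under Patient Characteristics, and a paired test is within-woman, so it cannot compete as a between-arm test. It is also the kind of test that reproduces n = 44.
- A reader might conclude that screening FSH was overlooked, or that HC3 ANCOVA on two values is simply better. Screening FSH has a stated purpose. The rank test on the two-value mean does about as well with equally correlated normal data, and better under equally correlated heavy tails. Neither is assured of a gain if screening is the weaker predictor. That is perhaps less likely, with screening within 14 days of registration and the outcome at day 85, but the protocol gives no correlations.

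**Conclusion.** The inconsistency is real and confined to wording: the synopsis and 8.2.6 leave open what 8.2.7 closes. Left open, it would cost about 1-3 points of type I error, and the two tests would disagree in about 9-17% of trials at the planned fall (normal data, r = 0.5-0.9).

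The precision gain is a worthwhile option and not the correction of an error. It is about 5-13 points for two-value HC3 ANCOVA if screening and baseline correlate equally with week 12 and data are normal. It is little or nothing under heavy tails, and about 7 points can be lost if screening tracks week 12 less well. In that case single-baseline HC3 ANCOVA is safer: with normal data it did not fall below the planned test beyond simulation error, though it is vulnerable to heavy tails.

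No choice among these rescues the between-arm comparison. Its power stays below 80% unless r is near 0.9, so a non-significant result must not be read as showing no FSH decline.

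**What to change.** 1. In the synopsis, 8.2.6 and 8.2.7, state one prespecified primary between-arm test with no condition attached. Delete the clause on adjusting by initial value, and run the supporting analysis whether or not linearity appears to hold.
2. Preferably use pre-dose FSH in that test. Either use ANCOVA of week-12 FSH with HC3 variance (not ordinary least squares, given 4:1 allocation), or a rank test on change from the screening-baseline mean. Keep the other as the sensitivity analysis. For the ANCOVA, decide in advance between the two-value mean and the single baseline, and state the downsides above. Keep the planned description of screening-to-baseline variation.
3. In 8.2.3, at most clarify that its sentence is not the between-arm FSH test. Do not remove the within-arm paired test that matches n = 44 in 8.1.
4. State that a non-significant between-arm result is not evidence of no decline.

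Cost: wording only, with no new samples, visits or patients. Changing the primary analysis requires a protocol amendment under 8.2.1. If change from a two-value mean is used, the endpoint wording in the synopsis, 2.2 and 6.1 must change too.
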